2.4. EFFICACY OUTCOMES

2.4.1. PRIMARY OUTCOME

The change in indexed left ventricular end-systolic volume (LVESVI) from baseline to the 12 month follow-up visit will be summarised overall and by randomised group and compared between randomised groups using a linear regression model adjusted for baseline LVESVI, diuretic use at baseline and time from baseline to the 12 month follow-up visit.

2.4.2. SECONDARY OUTCOMES

The following outcomes will be analysed as described in section 1.7.2:

- Change in NT-proBNP
- Change in hsTnI
- Change in other cardiac magnetic resonance imaging-based metrics of LV remodelling from baseline to 12 months follow-up:
 - Indexed LV end-diastolic volume (LVEDVI)
 - Indexed left atrial volume by body surface area (LAVI)
 - LV ejection fraction (LVEF)
 - LV mass index
- Change in patient well-being as assessed by a patient global assessment questionnaire at 12 months follow-up

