8.2.2 CMR protocol

All CMR scans will be performed on a single 3.0 Tesla Siemens MAGNETOM Prisma scanner located in the CRF at the QEUH. The MRI scan will include cine MRI, T1 and T2 maps, strain encoded MRI, and contrast enhanced imaging including first pass perfusion at rest, microvascular obstruction and late gadolinium enhancement imaging 10 - 15 min after contrast administration. IV access will be required for contrast administration and a full blood count will be obtained before the scan in order to measure extracellular volume. Specific details of the CMR protocol are detailed in a local Standard Operating Procedure. Patients will be provided with an MRI information sheet prior to their visit (Appendix 2).

8.3 26-week visit

This will comprise of a half-day visit to the QEUH CRF. A number of the baseline investigations will be repeated:

- full physical examination
- spot urine collection
- venepuncture – 50ml blood withdrawn for biochemical and hormonal analysis

Patients will also be asked to complete a short patient global assessment questionnaire (Appendix 3) at this visit.

8.4 52-week visit (+/- 3 months)

This will comprise of a half-day visit to the QEUH CRF. A number of the baseline investigations will be repeated:

- full physical examination
- spot urine collection
- venepuncture – 50ml blood withdrawn for biochemical and hormonal analysis
- cardiac MRI with gadolinium contrast will be performed.

Patients will also be asked to complete a short patient global assessment (Appendix 3) questionnaire at this visit.

In response to the COVID-19 pandemic we have allowed an extension of the patients IMP treatment by up to 3 months. During this extended time on IMP we would anticipate following up with patients by telephone every 6 weeks. Patients have the clinical research team contact details should they wish to discuss any aspect of the extended involvement themselves.

At this point a patient's participation in the involvement in the trial will end. They will return any unused study drug. Following their involvement in the trial patients will be converted to an ACE-inhibitor or ARB as per local practice guidelines at an equivalent dose to their final study drug dose level. Prior to commencement of any ACE-inhibitor, patients will require to have a 36-hour washout period following their last dose of study drug in order to reduce the risk of angioedema associated with combined ACE and NEP inhibition.

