11.3 Statistical analysis

The study will have a comprehensive Statistical Analysis Plan, which will be authored by the Trial Statistician and agreed by the Investigators before the final unblinded analysis. Analysis will be done on an intention-to-treat basis. The Robertson Centre for Biostatistics, functional unit of the Glasgow Clinical Trials Unit, a fully registered UK CRN Clinical Trials Unit, will manage and analyse trial data.

The primary analysis will compare LVESVI at 12 months between randomised groups using a linear regression model, adjusted for baseline LVESVI, and whether or not taking diuretics at baseline. Similar methods will be applied to secondary outcomes. Safety data will be summarised without formal statistical comparison.

12 Data handling

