1.7.2. GENERAL PRINCIPLES

Data will be summarised for all participants and by randomised treatment group where appropriate. Categorical variables will be summarised with the number of observations and missing values, and number and percentage of participants falling into each category. Continuous variables will be summarised using the number of observations and number missing, mean, standard deviation (SD), median, 25th and 75th quartiles (Q1 and Q3 respectively), minimum and maximum values. Rates of recruitment and retention will be summarised as counts and percentages with 95% confidence intervals.

All efficacy outcomes will be analysed using regression analysis models that are adjusted for the baseline value of the outcome in question and whether or not taking diuretics at baseline. Efficacy outcomes will be summarised at baseline, 12 months and for the change from baseline at 12 months, presented overall and by treatment group. The model's intervention group treatment effect (and 95% CI) and p-value will be presented for outcome results measured at 12 months. All biomarker outcomes will additionally be summarised at 6 months and for the change from baseline at 6 months. Furthermore, a repeated measures linear regression model will be performed for each biomarker outcome, adjusting for the main effects of time-point and randomised group and the interaction between time-point and randomised group. The intervention group

treatment effect and time-point effect (and 95% CIs) will be presented with p-values for these main effects and their interaction.

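### The SAP's rule for the patient global assessment needs a baseline value that the protocol never collects, so the prescribed model and two of the three prescribed summaries cannot be produced

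*SAP*

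**What the plan says.** SAP 2.4.2 names the outcome as "Change in patient well-being as assessed by a patient global assessment questionnaire at 12 months follow-up". It directs every outcome in that list to SAP 1.7.2 and makes no exception for this one.

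SAP 1.7.2 covers all efficacy outcomes. It prescribes "regression analysis models that are adjusted for the baseline value of the outcome in question and whether or not taking diuretics at baseline". It adds that "Efficacy outcomes will be summarised at baseline, 12 months and for the change from baseline at 12 months", and that the model's "intervention group treatment effect (and 95% CI) and p-value will be presented for outcome results measured at 12 months". Six-month summaries are assigned by name to one class only: "All biomarker outcomes will additionally be summarised at 6 months and for the change from baseline at 6 months".

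Protocol 11.3 has no rule specific to the questionnaire, only that "Similar methods will be applied to secondary outcomes".

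On collection, Protocol 8.3 (26-week visit) says "Patients will also be asked to complete a short patient global assessment questionnaire (Appendix 3) at this visit", and Protocol 8.4 (52-week visit) says "Patients will also be asked to complete a short patient global assessment (Appendix 3) questionnaire at this visit". Table 9-1 marks the questionnaire at Visits 7 and 9 and nowhere else. It is absent from the pre-randomisation investigations (Protocol 8.2) and from the baseline characteristics (SAP 2.3).

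**The concern.** The rule requires a quantity that the trial does not collect. This is more than missing detail: a stated model and two stated summaries cannot be carried out. The outcome is the only patient-reported one among the secondary endpoints.

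If the text stays as it is, somebody must decide outside the SAP what *change* means here, which model replaces the written one, and whether the earlier questionnaire plays any part. One of those choices would do harm. Week 26 is the only assessment before week 52, so it could be pressed into service as a baseline although it is measured after randomisation. SAP 2.4.4 carries all efficacy outcomes into three scan-timing subgroups, so the same unusable rule applies there too.

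**Working it through.** No figure in the plan is at issue. The sample size concerns LVESVI only: 45/(1 − 0.10) = 50 per arm, or 100 in total, which agrees with Protocol 11.1. The documents give no power or sample size for the questionnaire. The check is therefore a comparison of what the rule needs with what is collected.

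**Step 1: collection.** In Table 9-1 the questionnaire row has two marks, Visit 7 (week 26) and Visit 9 (week 52). Screening and Visit 1 are blank, so there are no pre-randomisation assessments.

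**Step 2: each requirement of SAP 1.7.2.**

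| Requirement | Data needed | Possible? |
|---|---|---|
| Summary at baseline | Pre-randomisation response | No |
| Summary at 12 months | Week-52 response | Yes |
| Summary of change from baseline | Both | No |
| Regression on own baseline and diuretic use | Week-52 response, baseline response, diuretic use | No |

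One of three summaries can be produced, and the model cannot be fitted. Leaving out the baseline term gives a comparison that can be fitted, but it is not the one written.

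**Step 3: does the unseen scale matter?** There are two possibilities for Appendix 3.
- *Transition item* (patients rate how they have changed): the 12-month response is itself the measure of change. There is no baseline value to adjust for or summarise, and no information is lost.
- *Current-status scale*: a change from baseline cannot be computed, because no starting value exists.

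The rule in 1.7.2 fails in both cases, so the finding does not depend on which applies.

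**Step 4: why week 26 cannot stand in.** Let treatment shift the mean response by d26 at week 26 and by d52 at week 52, with within-arm slope b of the later response on the earlier one. A model adjusted for week 26 estimates d52 − b × d26 for treatment, and a change score from week 26 estimates d52 − d26. Either removes some or all of an effect already present at week 26.

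**Step 5: what the remaining comparison rests on.** Randomisation makes the arms comparable at the start without a baseline term. Protocol 11.1 expects 10% discontinuation, from loss to follow-up, heart failure or death. If that rate also applied to this outcome, about 100 × (1 − 0.10) = 90 responses would remain. Those reasons plausibly relate to well-being, so absence of bias needs the added condition that missing responses are non-informative.

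**Step 6: randomisation factors.** Protocol 12.1 stratifies on diuretic use and on LVESVI (≤45 or >45 mL/m²). The primary model in SAP 2.4.1 includes both diuretic use and baseline LVESVI. The general model in 1.7.2 includes diuretic use only. In a linear model, leaving out a stratification factor with partial R² makes the standard error too wide by 1/√(1 − R²) − 1. At assumed R² of 0, 5, 10 and 20%, this is 0, 2.6, 5.4 and 11.8%. The documents give no R² for any of these outcomes, and the true value may be near zero. The effect is conservative, not a bias.

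**The case against.** The strongest reply is that this is one misplaced cross-reference. In Protocol 3.2 every other secondary endpoint is worded as running from baseline, and this one is not. In SAP 2.4.2 the MRI outcomes are worded from baseline, while the questionnaire is tied to 12 months only. That wording, together with a schedule that has no baseline questionnaire, is consistent with a transition item, for which nothing is lost. This stands as a plausible reading but not as proof, and the rule still would not fit.

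Second, a reader might infer that the model will be chosen after seeing results by arm. The documents do not support that. Protocol 12.1 keeps the allocation schedule from the statisticians until the database is locked and the analysis programs are validated, and SAP section 4 requires approval of tables and figures before lock. These safeguards reduce the risk of a data-driven choice. They do not put the choice in writing.

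Third, a reader might infer that the week-26 response is left without any use. SAP 1.7.2 opens with a general provision for summaries by treatment group where appropriate, and this already permits a descriptive table. Likewise, its reference to regression models in general leaves room for a model suited to the scale. Both points stand, so those parts of the fix clarify and do not repair.

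**Conclusion.** The point holds as a rule that cannot be carried out for one secondary outcome. The prescribed model and the baseline and change summaries are not producible. The 12-month summary is, and so is a 12-month comparison between arms without the baseline term. This rests on the text alone and not on the unseen content of Appendix 3. The primary analysis is unaffected.

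Three stronger readings go too far. The questionnaire is not unanalysable, because the 12-month comparison remains. It is not shown that a baseline assessment was forgotten or that information was lost, because a transition item needs none. Nor is the remaining comparison shown to be biased: it is unbiased under randomisation if missing responses are non-informative, and the documents do not settle that condition either way. No size can be given for any effect in the scan-timing subgroups, because the documents give neither their sizes nor the scale.

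**What to change.** Amend SAP 1.7.2 and 2.4.2 before database lock, with allocation still concealed. The documents do not show whether lock has occurred; if it has, record the same points as a documented departure.

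1. Exempt the questionnaire from the baseline covariate and from the baseline and change summaries. State that the week-26 response will not be used as a substitute baseline.
2. Define the endpoint as the 12-month response compared between arms. If Appendix 3 is a transition item, say that the response itself measures change. If it is a current-status scale, drop the word *change*.
3. Name a regression suited to the Appendix 3 scale (for example, proportional odds for ordered categories or linear for a numeric score), adjusted for the randomisation factors: diuretic use, and baseline LVESVI or its stratum. Summarise week 26 descriptively by arm.
4. Carry the same rule into SAP 2.4.4.

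The cost is SAP wording and no new data. If the scale measures current status, Protocol 3.2 and the synopsis also use *change*, so a wording amendment or a note to file is needed there.

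A separate improvement costs nothing in data: add baseline LVESVI or its ≤45/>45 stratum to the other full-population models under 1.7.2, because randomisation is stratified on it. The gain in precision may be near zero. The primary model needs no change.

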3.2 Secondary Endpoints

- Change in other cardiac magnetic resonance imaging-based metrics (indexed LV end-diastolic volume, LVEF, LV mass index) of LV remodelling from baseline to 12 (+/- 3 months) months.
- Changes in hsTnI from baseline to 12 (+/- 3 months) months.
- Changes in NT-proBNP from baseline to 12 (+/- 3 months) months.
- Change in patient well-being as assessed by a patient global assessment questionnaire.

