8.5 Definition of end of trial

The end of the trial is defined as the date of the last patient's 52-week (+/- 3 months) study visit plus additional 30 days of event reporting.

9 Assessment, samples and data collection

Trial data will be recorded on trial-specific eCRFs. Only the patient's unique identifier number, date of birth and initials will be recorded on the eCRF in order to identify the patient. Any missing or discrepant data queries will be sent to appropriate research

team member(s) to be reviewed. Biochemical samples will be stored in the QUEH Biochemistry department and the BHF Glasgow Cardiovascular Research Centre to be analysed in batches on completion of the trial. Analysis of echocardiograms and CMR imaging will be performed offline.

Table 9-1 Schedule of Assessments

Study Procedure	Screening (>3months post myocardial infarction)	Visit 1 - Randomisation (Week 0)	Visit 2 (Week 1 ± 3 days)	Visit 3 (Week 2± 3 days)	Visit 4 (Week 4± 3 days)	Visit 5 (Week 5± 3 days)	Visit 6 (Week 14 ± 7 days)	Visit 7 (Week 26 ± 7 days)	Visit 8 (Week 39 ± 7 days)	Visit 9 (Week 52 ± 3 months)
Review Inclusion/Exclusion Criteria	X									
Echocardiogram	X									
Obtain informed consent	X	X								
Cardiac MRI		X								X
Physical examination		X	X		X			X		X
Medical history	X	X								
Concomitant medications	X	X	X	X	X	X	X	X	X	X
Vital Signs (Blood pressure/Heart rate)	X	X	X	X	X	X	X	X	X	X
12 Lead ECG		X								
Spot urine collection		X						X		X
Venepuncture (Urea and Electrolytes/FBC and LFTs)	X&	X	X	X	X	X	X	X	X	X
Venepuncture (Biochemical/hormonal/biomarker analysis)		X						X		X
Pregnancy testing in WoCBP		X			X		X	X	X	X
Patient global assessment questionnaire								X		X
IMP Dispensing*		X			X		X	X		
Up-titrate IMP#					X					
IMP Administration+		X	X	X	X	X	X	X	X	X
Adverse event reporting			X	X	X	X	X	X	X	X
Study completion										X

* Study drug will be introduced at equivalent dose to existing ACE-i/ARB treatment (Dose level 2 or 3) at investigator's discretion

#Up-titration not required if patient already on dose level 3 but down titration to dose level 2 permitted in response to COVID-19

&If not done in the preceding 6 months

+Emergency IMP dispensing permitted during COVID-19 pandemic

10 Pharmacovigilance

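### The patient global assessment is collected at weeks 26 and 52, but no pre-specified SAP output uses the week-26 score

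*SAP*

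**What the plan says.** **Collection.** Protocol 8.3 (26-week visit) states: "Patients will also be asked to complete a short patient global assessment questionnaire (Appendix 3) at this visit". Protocol 8.4 (52-week visit) has the matching sentence: "Patients will also be asked to complete a short patient global assessment (Appendix 3) questionnaire at this visit". In the schedule of assessments (Protocol Table 9-1) the PGA row is marked at Visit 7 (week 26) and Visit 9 (week 52) only, with no mark at screening or Visit 1.

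**Endpoint.** Protocol 3.2 lists "Change in patient well-being as assessed by a patient global assessment questionnaire" with no time point. The neighbouring secondary endpoints do carry one, for example "Changes in NT-proBNP from baseline to 12 (+/- 3 months) months".

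**Analysis.** SAP 2.4.2 lists "Change in patient well-being as assessed by a patient global assessment questionnaire at 12 months follow-up" and sends it to SAP 1.7.2. That section says: "Efficacy outcomes will be summarised at baseline, 12 months and for the change from baseline at 12 months, presented overall and by treatment group". It then adds: "All biomarker outcomes will additionally be summarised at 6 months and for the change from baseline at 6 months". A repeated-measures linear model follows, again for biomarker outcomes. No other SAP section names an output for the week-26 PGA.

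**The concern.** NT-proBNP and hsTnI are sampled at the same two follow-up visits as the PGA, and the SAP gives them a 6-month summary and a two-visit model. The PGA gets neither, and the SAP gives no reason for the difference. Half of the scheduled PGA assessments therefore inform no planned comparison.

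Two things are at stake:

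- **Patients lost between the visits.** A patient who completes the week-26 questionnaire but not the week-52 one contributes nothing to the planned PGA comparison. If the chance of being lost depends on how the patient felt at week 26, and differs between arms, a 12-month comparison of those remaining is biased. The week-26 score is the PGA information that could reduce that bias.
- **Timing.** In Table 9-1 the week-26 window is 7 days either side, whereas week 52 allows 3 months either side. The more tightly timed PGA is the one with no planned output.

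**Working it through.** **1. Which outputs use the week-26 PGA?**

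| Place | Week 26 | Week 52 |
|---|---|---|
| Protocol 8.3, 8.4 and Table 9-1 (collection) | yes | yes |
| Protocol 3.2 (endpoint) | no time point stated | no time point stated |
| SAP 2.4.2 (PGA outcome) | not named | yes |
| SAP 1.7.2, efficacy summaries and model | not named | yes |
| SAP 1.7.2, 6-month summaries and repeated-measures model | biomarkers only | biomarkers only |

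The PGA is a questionnaire, not a biomarker. The count of pre-specified outputs that use the week-26 PGA is 0. SAP 1.8 mentions listings but does not itemise them.

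**2. The plan's own figures.** The documents give no precision or power figure for the PGA. The only stated calculation is for the primary endpoint (Protocol 11.1). It reproduces: 45 per group, difference 6 mL/m², SD 7.8 mL/m², two-sided 0.05 gives power of 95.4% (normal) or 95.0% (t), consistent with the stated figure of more than 90%; and 90/(1 − 0.10) = 100. It supplies only the 50 randomised and 45 completing per arm used below.

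**3. Precision of the 12-month contrast.** Assumptions, none from the documents: a roughly continuous score, equal variance at both visits, and within-patient correlation ρ from 0.4 to 0.7. Suppose all 50 per arm have a week-26 score, 45 have a week-52 score, and both visits enter one model. In units of the score variance:

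- Variance with week 26 = 2 × [ρ²/50 + (1 − ρ²)/45]
- Variance without week 26 = 2/45
- Ratio = 1 − ρ² × (1 − 45/50) = 1 − 0.1ρ²

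| ρ | Variance ratio | SE reduction |
|---|---|---|
| 0.4 | 0.984 | 0.8% |
| 0.5 | 0.975 | 1.3% |
| 0.6 | 0.964 | 1.8% |
| 0.7 | 0.951 | 2.5% |

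This is an upper limit, because it puts all the loss after week 26. If half of the 10% is lost earlier, 47.5 per arm have a week-26 score. The ratio becomes 1 − ρ² × (1 − 45/47.5), and the SE reduction is 0.4% to 1.3%.

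**4. Bias if loss depends on the week-26 score.** As an illustration, let the worst-scoring 14% in one arm and 6% in the other (average 10%) leave after week 26. For a normal score, dropping the lowest fraction p raises the mean of those remaining by φ(z_p)/(1 − p) SD at week 26, and by ρ times that at week 52.

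- p = 0.14: 0.2226/0.86 = 0.259
- p = 0.06: 0.1191/0.94 = 0.127
- Difference = 0.132 SD at week 26
- At week 52: 0.5 × 0.132 = 0.066 and 0.7 × 0.132 = 0.092, so about 0.07 to 0.09 SD; at ρ = 0.4, about 0.05 SD

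With 7% against 3% the week-26 difference is 0.144 − 0.070 = 0.074 SD, which gives about 0.04 to 0.05 SD at ρ = 0.5 to 0.7. A correctly specified two-visit likelihood model removes this bias when loss depends only on the observed week-26 score and the other terms in the model.

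**The case against.** **Choosing 12 months is not a fault.** Protocol 11.3 compares the primary outcome at 12 months and applies similar methods to secondary outcomes, and the other secondary endpoints in Protocol 3.2 are tied to 12 months. Settling one time point for an endpoint that the protocol left open is ordinary pre-specification. This stands. A reader might infer that the SAP departs from the protocol by restricting the PGA to 12 months; the documents do not support that.

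**The data are not excluded.** A reader might infer that the week-26 questionnaires are discarded. The SAP only names no output for them, and they may appear in the listings. With no baseline PGA, change might also be read as week 26 to week 52, which would use the score. The SAP does not say so, and SAP 1.7.2 speaks of change from baseline.

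**The scale is unknown.** Only the heading of Appendix 3 is available in the text reviewed, which is not a defect of the plan. The item may be ordinal, or may ask about change since the start. The figures above treat it as continuous, so they are indicative only.

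**A large efficiency gain is not available for the stated result.** The average of the two visits has an SE smaller by 1 − √((1 + ρ)/2), that is 16.3% at ρ = 0.4 and 7.8% at ρ = 0.7. In patient numbers, 2/(1 + ρ) − 1 gives 43% and 18% more. A reader might take these as the loss from ignoring week 26, but they belong to a different, supportive estimand.

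**The bias case is extreme.** No document says that the worst scorers leave or that the arms differ in loss. The 10% in Protocol 11.1 covers the whole trial and includes death, for which a modelled 12-month score has no clear meaning. Stopping study drug need not mean a missing questionnaire: SAP 2.2 separates withdrawal from medication and from follow-up. It would be wrong to conclude that the 12-month result will be biased.

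What survives is that no planned comparison uses week 26, although the SAP already applies a two-visit approach to outcomes measured at the same follow-up visits.

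**Conclusion.** The point holds as a minor, worthwhile improvement. Zero pre-specified outputs use the week-26 PGA, and that rests on the text alone. The benefit of using it is modest: at most about 1% to 2.5% smaller SE for the 12-month contrast, assuming correlation 0.4 to 0.7, equal variances, a roughly continuous score and 10% lost, all after week 26. There is also protection against bias when loss depends on the week-26 score. Under a deliberately severe pattern of differential loss that bias is about 0.07 to 0.09 SD at correlation 0.5 to 0.7; under milder loss it is smaller. The absence of a scheduled baseline PGA is a separate and larger gap, because SAP 1.7.2 calls for change from baseline and baseline adjustment. It limits how any PGA model can be written.

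**What to change.** In SAP 1.7.2 and 2.4.2, before unblinding:

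- Add the PGA to the outcomes summarised and compared between groups at 6 months.
- Analyse both visits in one repeated-measures model suited to the scale (ordinal if the item is ordinal), with treatment, visit, treatment-by-visit and baseline diuretic use. Include no baseline-PGA term, since none is scheduled.
- Keep the 12-month contrast as the secondary result and label the week-26 contrast as supportive.

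The cost is a few lines of SAP wording and one extra model. It needs no new data and adds no patient burden. The small downside is additional supportive estimates to report; fixing their status in advance prevents a later choice between time points.
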